The purpose of this protocol is to describe the emulation of the **FLAURA trial**.^{5,6} FLAURA was a Phase III, double-blind, randomised study assessing the efficacy and safety of AZD9291 (= osimertinib, 80 mg orally, once daily) versus a standard of care (SoC) Epidermal Growth Factor Receptor (EGFR) Tyrosine Kinase Inhibitor (TKI) (either gefitinib [250 mg orally, once daily] or erlotinib [150 mg orally, once daily]) in patients with locally advanced or metastatic EGFR sensitizing mutation (EGFRm+) Non-small Cell Lung Cancer (NSCLC) who are treatment-naïve and eligible for first-line treatment with an EGFR-TKI.

The primary trial estimate targeted for emulation is a hazard ratio (HR) for death (overall survival) of 0.80 (95% CI 0.64 to 1.00) with a median overall survival time of 38.6 months (95% CI 34.5 to 41.8) in the osimertinib group and 31.8 months (95% CI, 26.6 to 36.0) in the comparator group. Market availability of osimertinib began April 18, 2018 based on the progression-free survival (PFS) endpoint.

The PFS endpoint was published in the NEJM on November 18, 2017 (PMID 29151359).5

The OS endpoint was published in the NEJM on November 21, 2019 (PMID 31751012).6

5. Research question and objectives

The primary and secondary research question is summarized in Table 1.

A. Primary research question and objective

Table 1. Primary and secondary research questions and objective.

Objective:	To compare the overall survival [OS] in patients who initiated osimertinib versus patients who initiated erlotinib or gefitinib.			
Hypothesis:	Initiation of osimertinib improves overall survival time as compared to initiation of erlotinib or gefitinib			
Population (mention key inclusion-exclusion criteria):	 Age at least 18 years Locally advanced or metastatic Non-small Cell Lung Cancer (NSCLC) patients who receive treatment without curative intent The line of therapy for patients in EDB1 and EDB2 is implicitly advanced/metastatic because the line of therapy classification starts after their advanced/metastatic diagnosis in the respective database In EDB4, patients must explicitly have any evidence of a metastasis prior initiating Osimertinib, gefitinib or erlotinib. 			

	Adenocarcinoma histology		
	EGFR sensitizing mutation (any EGFRm+)		
	Treatment-naïve and eligible for first-line (1L) treatment with an EGFR-targeted tyrosine kinase inhibitor (TKI)		
	• ECOG 0 or 1		
Exposure:	Initiation of osimertinib		
Comparator:	Initiation of erlotinib or gefitinib		

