Outcome:	Time to all-cause mortality (OS)		
Time (when follow up begins and ends):	From the day of treatment initiation until death or last observed clinical activity/last sign of the patient being alive or data cut-off, whichever occurred earlier		
Setting:	1L EGFRm+ metastatic NSCLC		
Main measure of effect:	Primary: Hazard ratio (95% CI) for overall survival		
	Secondary: median overall survival time (difference) in % (95% CI)		

The emulation of the main protocol elements of the FLAURA is illustrated side by side in **Table 2**.

Table 2. Trial emulation table summarizing the main protocol elements of the FLAURA trial and the planned emulation.

Protocol component	FLAURA RCT	Emulation	
Eligibility criteria	 - Age at least 18 years at time of randomization - Adenocarcinoma of the lung - Locally advanced or metastatic NSCLC, not amenable to curative surgery or radiotherapy - Tumour harbours one of the 2 common EGFR mutations known to be associated with EGFR-TKI sensitivity (Ex19del, L858R), either alone or in combination with other EGFR mutations - Patients must be treatment-naïve for locally advanced or metastatic NSCLC and eligible to receive first-line treatment with gefitinib or erlotinib 	there needs to be evidence of metastatic disease at time of treatment initiati (EDB4) - Evidence of any EGFR mutation in the 180 days before/on treatment initiati - Treatment needs to be first-line for advanced (EDB1) or metastatic (EDB2) disease or patients with prior exposure to any potential antineoplastic treatment	
Treatment	 World Health Organization Performance Status of 0 to 1 No prior treatment with any systemic anti-cancer therapy for locally advanced/metastatic NSCLC No prior treatment with an EGFR-TKI. osimertinib versus SoC EGFR-TKI (erlotinib or gefitinib) 	osimertinib versus SoC EGFR-TKI (erlotinib or gefitinib)	
strategies Assignment procedures	Random assignment to receive either osimertinib or SoC EGFR-TKI (gefitinib or erlotinib) in a 1:1 ratio	1:1 matching of patients based on their propensity to initiate osimertinib as opposed to SoC EGFR-TKI	
Follow-up period	Time from randomization until death from any cause or censoring of patients who did not die on the basis of the last recorded date that the patient was known to be alive	Time from treatment initiation until death from any cause or censoring of patients who did not die on the basis of the last recorded date that the patient was known to be alive	
Outcome	Overall survival	Overall survival	

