6.6.7. Context and rationale for covariates

We identified a series of covariates that are strong prognostic factors for the outcome and auxiliary covariates which may be useful to impute missing data. Such covariates comprise demographics, covariates indicating disease-severity, cancer-specific covariates as well as pathological and genetic factors. In addition, selected labs and vitals are considered since they were shown to carry a high amount of prognostic information as described in Becker, Weberpals, et al.¹⁰ For these variables, additional plausibility checks and transformations are carried out. In detail, labs and vitals are individually checked if they cross a certain biologically implausible threshold (e.g., a heart rate of 0) in which cases the values are set missing and imputed in a next step. These thresholds were compiled by experienced practicing physicians and medical oncologists and are listed in appendix **Table 10** and **Table 11**.

Note that not all covariates are available across all databases used for this trial emulation. In the analytical stage, the most comprehensive model will be fit for each database individually.

Table 5. Operational definitions of key covariates used for trial emulation.

Characteristic	Harmonized analysis variable name	R function to derive covariate (see pdf in appendix)	Details ¹	Variable encoding	Assessment window
Age at initial diagnosis	dem_age_initial_diagnosis	edbx_get_demographics()	Age measured at initial diagnosis of eligible primary tumor	Nominal (<60, 60-69, 70-79, 80+)	[-inf;0] at initial diagnosis of primary cancer
Age at index date	dem_age_index	edbx_get_demographics()	Age measured at index date	Binary (<60, 65+); modelled continuously in ROPRO ¹⁰	[0;0]
Sex	dem_sex	edbx_get_demographics()	Sex	Binary (Male, Female)	[0;0]
Year of index date	c_year_index	De novo derived from dt_index	Calendar year in which patient initiated study treatment	Nominal (<2018, 2018+)	[0;0]
Family history	dem_family_history	edbx_get_demographics()	Family history of cancer	Logical (TRUE, FALSE)	[0;0] (no specific date is associated)
Race	dem_race	edbx_get_demographics()	Race categorized as in the original RCT	Binary (Asian vs non-Asian)	[0;0]
Ethnicity	dem_ethnicity	edbx_get_demographics()	Ethnicity	Hispanic, Non-Hispanic	[0;0]
Region	dem_region	edbx_get_demographics()	US region patient receives care in; if given on a state level, region is manually mapped (see	Nominal (Northeast, South, West, Midwest)	[0;0]

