			Table 12)		
Practice type	dem_practice	edbx_get_demographics()	Setting patient is receiving care at	Nominal (academic, community, academic & community)	[-inf;0]
Socio-economic status	dem_ses	edbx_get_demographics()	Socioeconomic status (SES) index based on residence area of patient	Nominal (from '1 - Lowest SES' through '5 - Highest SES)	[-inf;0]
Smoking	c_smoking_history	edbx_get_demographics()	History of current or former (= TRUE) or never (= FALSE) smoking on or anytime before index date; if there are multiple records per patient, any evidence of former/current smoking is prioritized	Binary logical (TRUE, FALSE)	[-inf;0]
EGFR status	C_egfr_biomarker_status	edbx_get_biomarker()	Evidence of any EGFR mutation present. If patient has multiple measurements, any evidence of a mutation is prioritized. In case of ties, the closest measurement relative to index date is selected	Binary (negative, positive)	[-180;0]

Characteristic	Harmonized analysis variable name	R function to derive covariate (see pdf in appendix)	Details ¹	Variable encoding	Assessment window
ECOG	c_ecog	edbx_get_ecog()	ECOG performance status measured closest to index date within assessment window. In case of ties, the lower ECOG value is selected	Nominal (0, 1, 2, 3, 4); modelled as ordinal numeric in ROPRO ¹⁰ ; due to I/E criteria ECOG is modelled as a binary (0, 1) covariate	[-90;0]
Stage	c_stage_initial_dx	edbx_get_diagnosis_solid()	AJCC summary group stage at initial diagnosis	Ordinal numeric (from 0 to IV with sub-categories, e.g., IA1) ¹⁰	[-inf;0] at initial diagnosis of primary cancer
De novo metastatic status	c_de_novo_mets_dx	edbx_get_diagnosis_solid()	Evidence of presence of one or multiple metastases at/before initial diagnosis	Binary logical (TRUE, FALSE)	[-inf;0] at initial diagnosis of primary cancer
Evidence of metastases between initial diagnosis and index date	c_met_pre_index	edbx_get_diagnosis_solid()	Evidence of any metastasis between initial diagnosis and index date (includes the initial diagnosis and index date)	Binary logical (TRUE, FALSE)	[-initial dx;0]
Number of metastatic sites	c_number_met_sites	edbx_get_diagnosis_solid()	Number of metastatic sites for a given patient before/on index date	Integer	[-inf;0]
Time between initial diagnosis to index date	c_time_dx_to_index	edbx_get_diagnosis_solid()	Time in days between initial diagnosis to index date	Continuous	[-initial dx;0]

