Sensitivity #6	Restrict to patients with Exon19 deletion only (databases for which this information is available)	FLAURA only included patients with sensitizing mutation (Exon19 deletion) but this information is not consistently provided across databases which is why in primary analyses we include all patients with any EGFR mutation assuming that it is sensitizing given that these patients initiated osimertinib, gefitinib or erlotinib	Target population is genetically more identical and increases specificity of biomarker measurement	Information not consistently available
Sensitivity #7	Re-weighting of strong risk factors and/or treatment effect modifiers distribution to match that of FLAURA	In the presence of effect modification, treatment effect estimates may be different if	Re-weighting adjusts for differences in distributions of key risk factors and/or	Re-weighting risk factors/potential

		the distribution of strong risk factors/effect modifiers is different in the emulated cohort versus the trial cohort	treatment effect modifiers (see subgroup analysis in Table 7)	effect modifiers to match the FLAURA trial and simultaneously balancing them across treatment groups may be challenging due to differences in measurement
Sensitivity #8	Including patients who have had at least 1 visit 90 days prior to treatment initiation	EHR are often lacking data continuity, and this analysis uses the requirement of 1 visit as a proxy for continuous observation periods	Considers aspect of data continuity	There may be patients who are put on treatment immediately in which case they are falsely excluded
Sensitivity #9	Exclusion of patients with osimertinib exposure before April 18, 2018	There are a few patients who are observed to have received osimertinib before its official approval (potentially due to off-label use in 1L, compassionate use, etc.)	Limits chances of exposure misclassification	May exclude truly eligible patients
Sensitivity #10	Restriction of eligible calendar time period from 2015 to 2022	Descriptive analyses indicate that there was a rapid uptake of new initiators of osimertinib immediately after approval in 2018 and a sudden decrease of SoC TKIs. This means there is hardly any overlap of patients pre/post 2018 and calendar cannot be sufficiently balanced	This sensitivity aims to mitigate the potential effects by imbalance in calendar time	Calendar time will overall remain imbalanced

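### Table 5 lists no EGFR mutation-subtype covariate; its one genetic entry is constant in the EGFR-mutated cohort, and the stated reason for leaving subtype out does not fit a primary model run in EDB1 alone

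*Protocol*

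**What the plan says.** Section 6.6.7 of the protocol states that the covariates include "cancer-specific covariates as well as pathological and genetic factors", and that each database will get the fullest model its variables allow. Table 5 then has one genetic row, EGFR status. It is coded "Binary (negative, positive", is assessed from 180 days before index to index, and follows the rule "If patient has multiple measurements, any evidence of a mutation is prioritized".

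The population in Table 1 (section 5) is defined by "EGFR sensitizing mutation (any EGFRm"+). In Table 2 the emulation column asks for any EGFR mutation within 180 days up to treatment start. The trial column asks for one of two named mutations: ("Ex19del, L858R), either alone or in combination with other EGFR mutations".

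Subtype appears once more, in sensitivity analysis #6 (Table 9): "Restrict to patients with Exon19 deletion only (databases for which this information is available"). That row explains that the information is unevenly recorded, and that therefore "in primary analyses we include all patients with any EGFR mutation assuming that it is sensitizing". Section 6.1.1 and Table 7 fix EDB1 as the only database for the primary analysis.

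**The concern.** The plan promises adjustment for genetic factors, but the one variable it lists cannot differ between patients in the cohort. The primary analysis may therefore combine Ex19del, L858R and other EGFR mutations without balancing them or checking their balance.

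The arms are largely separated in time. Section 7 says calendar year predicts treatment perfectly, and sensitivity analysis #10 says there is hardly any overlap before and after 2018. If the mix of detected mutations changed over the years, that change would fall on the arm contrast. If subtype also bears on survival or on response to these drugs, the primary HR would carry confounding that a balance plot built from Table 5 would not show. The study exists to judge agreement with a trial HR of 0.80 (0.64 to 1.00), so even a modest shift matters.

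**Working it through.** **1. Can EGFR status vary in the cohort?** The eligibility rule (Table 2) and the covariate (Table 5) use the same definition, any EGFR mutation, and the same window. Every patient with an observed result is therefore positive. Section 6.7.1 keeps patients with missing values in the attrition steps, so some may have no result. Imputation can draw only on observed values, all positive. The variance is 0 before and after imputation, so the row adds nothing to the propensity score and its standardized difference cannot reveal imbalance.

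**2. Does the stated reason cover the primary analysis?** Sensitivity #6 argues from uneven recording across databases. That would support a common definition in a multi-database analysis. The primary model uses EDB1 only, and section 6.6.7 allows covariates to differ by database. The question that matters is whether EDB1 records subtype, and the protocol does not answer it.

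**3. Do the other planned analyses fill the gap?** Sensitivity #6 restricts to Exon 19 deletion. Subtype mix cannot confound within that subset, but L858R is dropped. The row also describes the trial's mutation criterion as Exon 19 deletion, whereas Table 2 names both Ex19del and L858R. A different HR in #6 could reflect a different population or confounding, and #6 does not show subtype balance in the primary cohort. Sensitivity #7 refers to the Table 7 subgroups (sex, age, race, smoking, ECOG), which do not include subtype.

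**4. How large could a shift be?** The protocol gives no figure on subtype, so there is none to reproduce. Assumptions: a binary worse-prognosis subtype, prevalence p1 under osimertinib and p0 under SoC, death HR h, true HR 0.80.

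Observed HR ≈ 0.80 × (1 + (h − 1)p1) / (1 + (h − 1)p0)

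This is an early-follow-up approximation, since the mix among survivors changes later. With prevalences centred on 50%, each cell gives the observed HR when the subtype is rarer under osimertinib / commoner under osimertinib:

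| Gap (points) | Standardized difference | h = 1.2 | h = 1.5 | h = 2.0 |
|---|---|---|---|---|
| 5 | 0.10 | 0.793 / 0.807 | 0.784 / 0.816 | 0.774 / 0.827 |
| 10 | 0.20 | 0.786 / 0.815 | 0.769 / 0.833 | 0.748 / 0.855 |
| 15 | 0.30 | 0.778 / 0.822 | 0.753 / 0.849 | 0.724 / 0.884 |

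Example: gap 15, h = 2.0, p1 = 0.425, p0 = 0.575 gives 1.425/1.575 = 0.905, and 0.80 × 0.905 = 0.724.

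For a rarer group (mutations other than Ex19del and L858R) with h = 2.0:
- 5% versus 10%: 1.05/1.10 = 0.955, giving 0.764, or 0.838 reversed.
- 5% versus 15%: 1.05/1.15 = 0.913, giving 0.730, or 0.876 reversed.

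**5. Scale.** The trial interval implies a standard error of log HR of ln(1.00/0.64)/3.92 = 0.114. The centred-50% shifts run from |ln 0.991| = 0.009 to |ln 0.905| = 0.100, which is about 0.08 to 0.88 of that standard error.

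**The case against.** The strongest reply has five parts.

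- **The EGFR row is legitimate.** Table 5 mixes eligibility variables with adjusters; histology is another flag of this kind. This stands. A reader might infer that the row is an error, but the fault is only that no other genetic variable is listed.
- **The fitted covariates cannot be seen.** Figure 9, which shows the propensity covariates, is not reproduced in the text at hand. This stands, so the point concerns what Table 5 lists. It does not establish what the fitted model contains.
- **Feasibility in EDB1 is not established.** No database with subtype data is named. This stands. A reader might infer that EDB1 holds subtype and the plan ignores it; the protocol does not say so.
- **The choice is disclosed and probed.** Sensitivity #6 states the assumption and restricts to one subtype, which avoids imputing subtype. This stands in part: subtype is not ignored, but #6 does not examine the primary cohort, and its rationale does not fit a single database.
- **The bias route is not documented.** Nothing says that subtype mix changed over time or differs by arm, and section 7 assumes that calendar year affects outcome only through treatment. Table 2 groups Ex19del and L858R together as sensitizing, so it cannot be read as implying that one has worse survival. At most it separates these two from other mutations. This stands, and it limits what can be said about size.

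**Conclusion.** The point holds as a gap in the listed adjustment set. As Table 5 stands, no genetic factor is adjusted for, although the primary analysis accepts any EGFR mutation and the plan indicates that some databases record Exon 19 deletion. The reason offered does not justify the omission from an EDB1-only model.

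A reader might go further and conclude that the primary HR is biased, or biased in favour of osimertinib. The protocol does not support that. It gives no subtype distribution by arm and no prognostic effect. The range of 0.72 to 0.88 around a true 0.80 rests wholly on assumed prevalences and subtype HRs, and either direction is possible. It shows that an imbalance could matter, not that one exists. The change is worth making before analysis because it is cheap where the data exist. Confidence is moderate, mainly because EDB1 availability is not stated.

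**What to change.** 1. State in section 6.6.7 which databases record EGFR mutation subtype, and say explicitly whether EDB1 does.
2. In each database that records it, add to Table 5 a covariate *EGFR mutation subtype (Ex19del / L858R / other)*. Use it in the imputation model, the propensity model and the balance plots.
3. If EDB1 does not record it, list subtype in section 7 as an unmeasured potential confounder.
4. Reconcile the description of the trial's mutation criterion in sensitivity #6 with Table 2.

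Extending the re-weighting in sensitivity #7 to subtype is not proposed, because it would need the trial's subtype distribution, which the protocol does not give.

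The cost is one covariate derivation per database and some wording. Where subtype is often unrecorded, imputing it adds noise. Where EDB1 lacks it, only the section 7 text changes and the primary estimate stays as planned.

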		appendix)			
Heart rate ²	c_hr_cont	edbx_get_vitals()	Closest heart rate measurement	continuous	[-90;0]
			(in bpm) relative to index date. In		
			case of ties, the lower is selected		
Oxygen saturation	c_oxygen_cont	edbx_get_vitals()	Closest heart rate measurement	continuous	[-90;0]
		- "	(in bpm) relative to index date. In		
			case of ties, the lower is selected		

¹x stands for the pseudonymized number of the respective database, i.e., EDB1, EDB2 or EDB4

[figure not shown]
6.7. Data analysis

6.7.1. Context and rationale for analysis plan

To emulate the FLAURA trial, the following analytical workflow will be used (Figure 4). First, an analytical cohort with covariates on key eligibility criteria and prognostic factors will be derived across all databases. To ensure reproducibility and consistency throughout the entire ENCORE project, the internally developed *encore.io* R package streamlines this process using the functions referenced in Table 5. Operational definitions of key covariates used for trial emulation. Table 5 (code documentation see appendix). The analytical cohort will be derived by first identifying an advanced NSCLC inception cohort of initiators of osimertinib, erlotinib or gefinitib in the first line setting as described in section 6.6.4. Next, key eligibility criteria will be applied in which patients with missing values are considered eligible in the respective attrition steps to allow thorough missing data investigations.

² For calculation of ROPRO prognostic score¹⁰, this variable is log transformed.

³ For calculation of ROPRO prognostic score¹⁰, this variable is log-log transformed.

Once a full analytic cohort is built, principled missing data investigations will be employed to empirically assess assumptions on potentially underlying missingness mechanisms according to Rubin's classification of missing data (i.e., missing completely at random [MCAR], missing at random [MAR] and missing not at random [MNAR]).¹⁶ To that end, we will adopt a principled process on missing data that was developed as part of a FDA Sentinel Innovation Center causal inference workstream that empirically evaluates different aspects across partially observed covariates based on three group diagnostics (Table 6).^{17,18} In brief, the first group diagnostics computes distributions and absolute standardized mean differences (ASMD) between patients with and without an observed value for a given partially observed covariates. If missingness can be explained by observed covariates such as in MAR mechanisms, patient characteristics will significantly differ which will (in analogy to propensity scores) be indicated by ASMDs > 0.1. In addition, Hoteling's¹⁹ and Little's²⁰ tests additionally provide formal hypothesis tests for such comparisons in which high test statistics and a rejection of the null hypothesis would provide evidence for differences in the distribution of patient characteristics and suggest the underlying mechanism is not MCAR or MNAR. Group 2 diagnostics assess the ability to predict missingness based on observed covariates by fitting a classification model to predict the missingness indicator of the partially observed covariate. To that end, we will fit a random forest (RF) classification model using observed covariates with a 70/30 train-test split of the complete cohort. A sufficiently high area under the receiver operating characteristic curve (AUC) metric of the test dataset may demonstrate that missingness can be predicted well and could point towards MAR as a likely mechanism as opposed to an AUC~0.5 which would suggest MCAR or MNAR. Group 3 diagnostics evaluates the association between the missingness indicator of the partially observed covariates and the outcome (OS). If the missingness of a confounder cannot be explained or approximated by observed covariates and a difference in the outcome is observed depending on the missingness indicator (e.g., $HR_{missingness\ indicator} \neq 1$), this may be indicative of an underlying MNAR mechanism. These empirical diagnostics will be implemented through the smdi R package²¹ and be further enhanced by clinical expert knowledge.

Table 6. Diagnostics to empirically differentiate and characterize missing data mechanisms.

Group 1 Diagnostics			Group 2 Diagnostics	Group 3 Diagnostics
Diagnostic metric	Absolute standardized mean difference (ASMD)	P-value Hoteling ¹⁹ / Little ²⁰	Area under the receiver operating curve (AUC)	Log HR (missingness indicator)
Purpose	Comparison of distribution vs. without observed valuable observed covariate.	-	Assessing the ability to predict missingness based on observed covariates.	Check whether missingness of a covariate is associated with the outcome (differential missingness).
Example value	ASMD = 0.1	p-value < 0.001	AUC = 0.5	log HR = 0.1 (0.05 to 0.2)
Interpretation	≤0.1a: no imbalances in observed patient characteristics; missingness may be likely completely at random or not at random (~MCAR, ~MNAR). ≥0.1a: imbalances in observed patient characteristics; missingness may be likely at random (~MAR).	High test statistics and low p-values indicate differences in baseline covariate distributions and null hypothesis would be rejected (~MAR).	AUC values ~ 0.5 indicate completely random or not at random prediction (~MCAR, ~MNAR). Values meaningfully above 0.5 indicate stronger relationships between covariates and missingness (~MAR).	No association in either univariate or adjusted model and no meaningful difference in the log HR after full adjustment (~MCAR). Association in univariate but not fully adjusted model (~MAR). Meaningful difference in the log HR also after full adjustment (~MNAR).

Abbreviations: ASMD = Median absolute standardized mean difference across all covariates, AUC = Area under the curve, CI = Confidence interval, MAR = Missing at random mechanism in which the missingness probability depends on observed covariates, MCAR = Missing completely at random mechanism in which each patients has the same missingness probability, MNAR(unmeasured) = Missing not at random mechanism in which the missingness can only be explained by a covariate which is not observed in the underlying dataset, MNAR(value) = Missing not at random mechanism in which the missingness just depends on the actual value of the partially observed confounder of interest itself.

[figure not shown]
^a Analogous to propensity score-based balance measures.^{22a} Analogous to propensity score-based balance measures.²²

[figure not shown]
While the MAR assumption is a strong assumption to hold across all considered covariates, it was shown that especially in the context of partially observed covariate data (as opposed to missing exposure and outcome data), only mechanisms in which a covariate causes its own missingness leads to critical bias (MNAR).²³ In such situations, multiple imputation can have significant advantages over a complete case analysis since additional information (auxiliary covariates and missing indicator variables) can be included in imputation algorithms which can make the MAR assumption holding more plausible and increase efficiency in treatment effect estimates since all patients and critical covariates can be retained and variances can be realistically estimated, considering both the general sampling error and the error introduced by missing data.^{24,25} Hence, multiple imputation with flexible, non-parametric random forest imputation algorithms²⁶ (mice R package²⁷) will be used for this trial emulation. The number of imputed datasets (*m*) will be determined for each database separately based on the average proportion missingness observed in the analytic cohort and results from the above-referenced missing data investigations will inform the choice of appropriate sensitivity analyses.

Figure 5. Covariate balance across imputed datasets (simulated example).

Covariate Balance

Range across imputations

To estimate the treatment effects for osimertinib using propensity score matching across imputed datasets we will apply the "within" approach using the "MatchThem" R package. 28,29 That is, propensity score matching and the estimation of the treatment effect are performed in each imputed dataset separately and resulting treatment effect estimates are combined using Rubin's rule. In this study, this will be implemented by matching eligible patients on their propensity to initiate osimertinib using a 1:1 nearest neighbor matching algorithm without replacement and a caliper of 1% of the standard deviation of the propensity score. The resulting covariates balance will be assessed by computing and visualizing ASMDs before and after matching across datasets. As compared to a single dataset matching approach, this can lead to a range of ASMDs per covariate due to random variation across imputed datasets for which an example (using simulated data) is illustrated in Figure 5. If sufficient balance can be established, a Cox proportional hazards regression model will be fit to estimate the marginal average treatment effect in the matched population. Since in most databases there are more osimertinib patients than patients in the control arm, the estimand will rather correspond to the ATC than the ATT. Confidence intervals will be estimated using cluster-robust standard errors. 30 As a secondary endpoint, we will additionally estimate the median OS survival time difference between the two exposure groups using the Kaplan-Meier method. It should be noted that due to administrative and de-identification purposes, the date of death is often only available at the month- or year-granularity level, in which case the date of death will be imputed to the 15th of a month or July 2nd of a year, respectively (depending on the database). In rare cases, this can lead to negative/implausible follow-up times if the date of death is very close to the index date. These patients will be excluded from the analysis.

The final hazard ratio and median OS survival time difference estimates for each database will then be combined using Rubin's rule.^{27,31} To arrive at a single estimate across databases, the final estimates will be summarized through a meta-analytic fixed effects model.³² A summary of the analytic approach is summarized in Table 7 and an example workflow with simulated data and annotated code can be found https://example.com/here/beta-arrive

A. Primary analysis

Table 7. Primary and subgroup analysis specification

able 7. Primary and Subgroup	7 dilarysis specification
Hypothesis:	Initiation of osimertinib decreases the hazard of all-cause mortality as compared to initiation of erlotinib or gefitinib
Exposure contrast:	Initiation of osimertinib vs. initiation of erlotinib or gefitinib
Outcome:	Time to all-cause mortality (overall survival)
Databases used:	EDB1
Analytic software:	R 4.3.2. Version control of code and R packages will be established through git and Posit package manager, respectively. All packages are frozen to their most recent version as of April 24, 2024.
Model(s): (provide details or code)	See example code https://drugepi.gitlab-pages.partners.org/encore/flaura-nct-02296125/ (access only through MGB network for authorized personnel)
Confounding adjustment method	Name method and provide relevant details, e.g. bivariate, multivariable, propensity score matching (specify matching algorithm ratio and caliper), propensity score weighting (specify weight formula, trimming, truncation), propensity score stratification (specify strata definition), other. 1:1 propensity score nearest neighbor matching without replacement and a caliper of 1% of propensity score standard
Ministration of the	deviation
Missing data methods	Name method and provide relevant details, e.g. missing indicators, complete case, last value carried forward, multiple imputation (specify model/variables), other.
	Multiple imputation by chained equations using a random forest imputation model across all covariate types. The number of imputed datasets will be determined by the average proportion of missing values across all partially observed covariates. Imputation models will include all variables of the substantiative model, i.e., exposure, outcome, confounders/prognostic factors and additional auxiliary covariates.
Subgroup Analyses	List all subgroups
	In subgroup analysis, multiple imputation, propensity score matching and balance assessment will be conducted within each subgroup separately. The treatment effect will be estimated in the combined dataset by fitting a Cox proportional-hazards model that will include the exposure, the subgroup covariate of interest, and the treatment-by-subgroup interaction term. 1. Sex (Male, Female)
	2. Age (<65, ≥65)* 3. Resp (athricity (Agian Non Agian)*
	3. Race/ethnicity (Asian, Non-Asian)*4. Smoking history (current/former, never)5. ECOG (0, 1)*
	* indicates that a statistically significant differences were found in FLAURA

B. Secondary Analysis

Table 8. Secondary analysis specification.

ible of Secolidally allalysis sp	ecilication.
Hypothesis:	Initiation of osimertinib increases overall survival as compared to initiation of erlotinib or gefitinib
Exposure contrast:	Initiation of osimertinib vs. initiation of erlotinib or gefitinib
Outcome:	Median overall survival time, i.e., time until 50% of the patients in each stratum deceased
Databases used:	EDB1
Analytic software:	R 4.3.2. Version control of code and R packages will be established through git and Posit package manager, respectively.
Madal/a).	All packages are frozen to their most recent version as of April 24, 2024.
Model(s): (provide details or code)	See example code https://drugepi.gitlab-pages.partners.org/encore/flaura-nct-02296125/ (access only through MGB network for authorized personnel)
Confounding adjustment method	Name method and provide relevant details, e.g. bivariate, multivariable, propensity score matching (specify matching algorithm ratio and caliper), propensity score weighting (specify weight formula, trimming, truncation), propensity score stratification (specify strata definition), other.
	1:1 propensity score nearest neighbor matching without replacement and a caliper of 1% of propensity score standard deviation
Missing data methods	Name method and provide relevant details, e.g. missing indicators, complete case, last value carried forward, multiple imputation (specify model/variables), other.
	Multiple imputation by chained equations using a random forest imputation model across all covariate types. The number of imputed datasets will be determined by the average proportion of missing values across all partially observed covariates. Imputation models will include all variables of the substantiative model, i.e., exposure, outcome, confounders/prognostic factors and additional auxiliary covariates.
Subgroup Analyses	List all subgroups
	None; no subgroup-specific median overall survival estimates are reported for FLAURA.

Table 9. Sensitivity analyses - rationale, strengths and limitations.

	What is being varied? How?	Why? (What do you expect to learn?)	Strengths of the sensitivity analysis compared to the primary	Limitations of the sensitivity analysis compared to the primary
Sensitivity #1	Caliper matching on ROPRO prognostic score instead of propensity score	Matching patients on validated prognostic score may be more beneficial to control for (unmeasured) confounding	Matches patients on validated prognostic score that incorporates weights of key prognostic factors	Limited experience on how to optimally use prognostic scores and should be seen as an experimental sensitivity analysis
Sensitivity #2	ATO weighting instead of matching	Weights that resemble the average treatment effect in the overlap population (ATO) create a clinical equipoise population which is comparable to an RCT	ATO weighting usually results in excellent balance and clinical equipoise	Estimates the average treatment effect among the overlap patients which may not be comparable to target population anymore
Sensitivity #3	SMR/ATT weighting instead of matching. Here symmetric trimming (i.e., setting all weights lower/higher than that at a given quantile to the weight at the quantile) of extreme weights may be considered with the quantiles chosen based on weight distribution and resulting balancing performance.	SMR weighting retains all patients and resembles the same estimand as matching	ATT weighting retains all patients	Patients with extreme weights after trimming may bias the analysis
Sensitivity #4	Censoring date is changed to 3 months before data cut- off date	For all databases, information on mortality comes from different data sources which are updated asynchronously. To account for the potential lag of updated mortality information (ghost-time	Approach implements a more conservative censoring rule	Approach addresses ghost-time bias by censoring patients without a recorded

		bias ³³), the censoring date for patients without mortality event in the whole patient identification period will be moved to last sign of patients being alive/visit or 3 months before data cut-off date, whichever occurred earlier. ³⁴		death event earlier
Sensitivity #5	Delta imputation models for MNAR (tipping point analysis)	Primary multiple imputation analysis assumes MAR which may not hold for every covariate	Estimates impact of deviations from MAR assumption on final treatment effect estimates for key covariates	Delta parameters must be assumed and results are complex to interpret in multivariate missingness settings; just must important covariates or those with highest suspicion of being MNAR will be evaluated
